#### 4.7.4.2 Solicited Adverse Events

Solicited AEs are those events specifically sought for and recorded by the parent(s)/guardian(s) in the 7-Day Diary, entered on the day of vaccination and the subsequent 6 days.

Solicited Local AEs include pain, induration/swelling, and erythema/redness. All solicited local AEs will be assessed as related to the Study Vaccine.

Solicited Systemic AEs include fever (temperature  $\geq 37.5^{\circ}\text{C}$ ), nausea and/or vomiting, and diarrhea. For subjects less than 36 months of age at the time of the first dose of study vaccine solicited Systemic AEs also include loss of appetite and irritability. For subjects 36 months of age and older at the time of the first dose of study vaccine solicited Systemic AEs also include headache, myalgia, and malaise and fatigue.

For all solicited AEs the following summaries will be presented by treatment group. In addition, the summaries will be presented by dose (i.e. After 1st Vaccination, After 2nd Vaccination):

- The number and percentage of subjects reporting at least one occurrence of each type of adverse event will be presented with 95% CIs.
- The number and percentage of subjects experiencing at least one local reaction will be presented with 95% CIs.
- The number and percentage of subjects experiencing at least one systemic adverse event will be presented with 95% CIs.

For each of these summaries the relative risk and 95% CIs will be presented for Seqirus QIV/Comparator QIV.

All summaries will be presented overall and by maximum intensity. Analyses by treatment group will be repeated by age strata, by gender, by race, and by ethnicity where specified.

Separate summaries will be presented for Related Solicited Systemic Adverse Events, overall and by maximum intensity after any vaccination.

For all solicited events, the day of onset will be determined according to the day they are first recorded (day 1 to day 7). Summaries will be presented with the number (and percentage) of subjects experiencing at least one event by onset day.

For all solicited events, the duration (in days) will be determined as the number of consecutive days where severity is  $\geq 1$ . A subject may experience multiple events of a solicited AE. Separate events will be defined as  $\geq 1$  day without the event being recorded. Summaries will be presented with the number (and percentage) of subjects experiencing at least one event by duration. Number of events will also be presented.

Summaries of onset and duration will be presented by treatment group and repeated by age strata. In addition, the summaries will be presented by dose.

Severity will be determined as follows:

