From the model an adjusted difference in least square means (on the log scale) will be produced with 95% confidence limits. The estimated difference and the confidence limits will be back transformed to obtain an *adjusted GMT ratio* with 95% confidence limits. Each of the four strains will be analyzed separately. The adjusted GMT ratio will be the result for which the noninferiority assessment will be based on. The measure of the *unadjusted* GMT ratio based on postvaccination GMTs only will also be presented.

Secondary Objectives:

Secondary objectives include assessing the safety and tolerability of Seqirus QIV in two age strata: 6 months through 35 months and 36 months through 59 months of age, as well as overall.

The proportion of subjects with AEs in the two treatment arms will be presented. Adverse events will be monitored postvaccination as per the following:

1. Solicited local adverse reactions and systemic AEs through Day 7 (Days 1, 2, 3, 4, 5, 6, 7) after each vaccination dose;
2. Cellulitis-like reaction and cellulitis for 28 days after each vaccination dose;
3. Unsolicited AEs for at least 28 days following each vaccination dose;
4. Serious adverse events (SAEs) for at least 180 days following the last vaccination dose.

The frequency, duration and intensity of solicited and unsolicited AEs will be summarized for each age group and study vaccine. The proportion of subjects reporting each type of AE will be presented along with percentages and confidence intervals. Solicited local adverse reactions and systemic AEs will be summarized by frequency, duration and intensity. Unsolicited AEs will be summarized by body system and intensity. If sufficient numbers of cases of AEs occur, more formal statistical analyses of event rates or intensity may be conducted.

Further details of planned analyses will be specified in the Statistical Analysis Plan (SAP).

Statistical Considerations for Sample Size Calculations:

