- Parent(s)/guardian(s) will be issued with a digital thermometer and Local Reaction Measurement Card, and provided with electronic access to the 7-Day Diary (for recording solicited AEs), the Other Body Symptoms Diary (for recording unsolicited AEs), and the Medications Diary (for recording concomitant medications). The 7-Day Diary will be completed on the day of vaccination and for the subsequent 6 days following vaccination (total of 7 days). The Other Body Symptoms Diary and the Medication AE Diary will be completed on the day of vaccination until the next study visit.

- Parent(s)/guardian(s) will be reminded how to measure axillary temperature and record their child's temperature at the same time each evening, in addition to completing the diaries.
- Parent(s)/guardian(s) will be instructed to contact the Investigator/delegate immediately if the subject experiences any signs or symptoms with grade 3 intensity.
- Parents will be educated on how to recognize the signs/symptoms of an ILI and will be instructed to contact the investigator/delegate immediately if the subject experiences any signs or symptoms of an ILI from Day 1 until the Study Exit Visit.
- An appointment will be made for each subject to return to the clinic 28 + 4 days after Visit 1.

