Table 14.3.1.3.9	Solicited Systemic Adverse Events Overall and by Maximum Intensity: After Any Vaccination By Ethnicity

---

Table 14.3.1.3.10	Related Solicited Systemic Adverse Events Overall and by Maximum Intensity: After Any Vaccination
Table 14.3.1.3.11	Related Solicited Systemic Adverse Events Overall and by Maximum Intensity: After Any Vaccination By Age Strata
Table 14.3.1.3.12	Related Solicited Systemic Adverse Events Overall and by Maximum Intensity: After 1st Vaccination
Table 14.3.1.3.13	Related Solicited Systemic Adverse Events Overall and by Maximum Intensity: After 2nd Vaccination
Table 14.3.1.3.14	Related Solicited Systemic Adverse Events Overall and by Maximum Intensity: After 1st Vaccination By Age Strata
Table 14.3.1.3.15	Related Solicited Systemic Adverse Events Overall and by Maximum Intensity: After 2nd Vaccination By Age Strata
Table 14.3.1.4.1	Day of First Onset and Mean Duration of Solicited Local Symptoms: After Any Vaccination
Table 14.3.1.4.2	Day of First Onset and Mean Duration of Solicited Local Symptoms: After Any Vaccination By Age Strata
Table 14.3.1.4.3	Day of First Onset and Mean Duration of Solicited Local Symptoms: After 1st Vaccination By Age Strata
Table 14.3.1.4.4	Day of First Onset and Mean Duration of Solicited Local Symptoms: After 2nd Vaccination By Age Strata
Table 14.3.1.5.1	Day of First Onset and Mean Duration of Solicited Systemic Symptoms: After Any Vaccination
Table 14.3.1.5.2	Day of First Onset and Mean Duration of Solicited Systemic Symptoms: After Any Vaccination By Age Strata
Table 14.3.1.5.3	Day of First Onset and Mean Duration of Solicited Systemic Symptoms: After 1st Vaccination By Age Strata
Table 14.3.1.5.4	Day of First Onset and Mean Duration of Solicited Systemic Symptoms: After 2nd Vaccination By Age Strata
Table 14.3.1.6	Cellulitis-Like Reaction
*Table 14.3.1.7.1	Unsolicited Adverse Events by System Organ Class and Preferred Term
*Table 14.3.1.7.2	Unsolicited Adverse Events by System Organ Class and Preferred Term: By Age Strata
**Table 14.3.1.7.3	Unsolicited Adverse Events by System Organ Class and Preferred Term: By Gender
**Table 14.3.1.7.4	Unsolicited Adverse Events by System Organ Class and Preferred Term: By Race
**Table 14.3.1.7.5	Unsolicited Adverse Events by System Organ Class and Preferred Term: By Ethnicity
*Table 14.3.1.8.1	Related Unsolicited Adverse Events by System Organ Class and Preferred Term

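### Solicited-event duration is capped by the 7-day diary, so the planned mean durations understate how long reactions last; censor events present on Day 7 and label any mean as within Days 1-7

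*SAP*

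**What the plan says.** SAP 4.7.4.2 defines solicited events as those the parent or guardian records "in the 7-Day Diary, entered on the day of vaccination and the subsequent 6 days". On onset it says "the day of onset will be determined according to the day they are first recorded (day 1 to day 7"). On length it says "the duration (in days) will be determined as the number of consecutive days where severity is" at least 1; one or more event-free days separate one event from the next. The text then plans counts: "Summaries will be presented with the number (and percentage) of subjects experiencing at least one event by duration".

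The table list in SAP 5.3.3 goes further. Tables 14.3.1.4.1 to 14.3.1.4.4 carry titles beginning with the one for the first table, "Day of First Onset and Mean Duration of Solicited Local Symptoms: After Any Vaccination". Tables 14.3.1.5.1 to 14.3.1.5.4 are the systemic counterparts, starting with "Day of First Onset and Mean Duration of Solicited Systemic Symptoms: After Any Vaccination". These summaries are split by treatment group, age stratum and dose.

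The Protocol Synopsis (Statistical Analyses, Secondary Objectives) says: "Solicited local adverse reactions and systemic AEs will be summarized by frequency, duration and intensity". The Safety Assessments text (Synopsis and Protocol 10.3) is narrower. It lists duration for solicited systemic events only, and only through Day 7; for local reactions it lists type, frequency and intensity.

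**The concern.** A reaction that outlasts the diary has an unknown end. The rule gives it the number of days seen and averages it with reactions that are known to have resolved. Swelling from Day 5 to Day 12 counts as 3 days. A reaction lasting two weeks from Day 1 counts as 7.

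Nothing else in the SAP text repairs this. Site-entered solicited data exist (SAP 3.5.2.3) but refer to the same seven days. The missing-data rule in SAP 4.11 fills blank days from their neighbours and cannot carry an event past Day 7. Neither document says that an event continuing past Day 7 is flagged, censored or given an end date for this derivation.

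At stake is a descriptive between-vaccine safety summary. A reader of a table headed mean duration will take it as how long reactions lasted, and will compare the two vaccines on it.

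**Working it through.** **Plan's own figure.** The documents state no expected duration and no expected share of events outlasting the diary, so there is nothing to reproduce.

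**Inputs from the documents.** Diary window 1 + 6 = 7 days per dose; onset Day 1 to 7; duration = consecutive days with severity at least 1 (all SAP 4.7.4.2).

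**Step 1: the cap (no assumption needed).** Recorded duration = min(D, c), where D is the true duration, d the onset day and c = 8 - d. For onset on Days 1 to 7 the cap is 7, 6, 5, 4, 3, 2, 1 days. A reaction whose last day is Day 7 is counted in full; one that continues to Day 8 or later is cut.

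**Step 2: illustration of size (assumed distributions).** Take geometric durations with mean m, and q = 1 - 1/m. For a given cap c, the tabulated mean is 1 + q + ... + q^(c-1) = m(1 - q^c), and the share cut off is q^c. Three onset patterns are assumed:

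- early: 70% Day 1, 25% Day 2, 5% Day 3
- intermediate: 50, 25, 10, 5, 4, 3, 3% on Days 1 to 7
- uniform: one seventh on each day

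Worked case, m = 3 (q = 2/3): tabulated means by onset day are 2.82, 2.74, 2.60, 2.41, 2.11, 1.67, 1.00.

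- Early: 0.70 × 2.82 + 0.25 × 2.74 + 0.05 × 2.60 = 2.79
- Uniform: 15.35 / 7 = 2.19

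| True mean (days) | Early: tabulated (cut off) | Intermediate | Uniform |
|---|---|---|---|
| 2 | 1.98 (1.1%) | 1.92 (4%) | 1.72 (14.2%) |
| 3 | 2.79 (7.0%) | 2.64 (12%) | 2.19 (26.9%) |
| 4 | 3.40 (15.0%) | 3.17 (21%) | 2.51 (37.1%) |
| 5 | 3.86 (22.9%) | 3.56 (29%) | 2.74 (45.2%) |

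The percentages are events continuing to Day 8 or later. Events merely present on Day 7 are more numerous: about 18% (m = 3) and 36% (m = 5) in the intermediate pattern.

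**Step 3: difference between vaccines, same onset pattern in both arms.** The shortfall m·q^c rises with m, so it is larger in the longer-lasting arm.

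- 2 v 3 days (true difference 1.0): recorded 2.79 - 1.98 = 0.81 (early), or 0.48 (uniform)
- 3 v 4 days (true difference 1.0): 0.61 (early), or 0.32 (uniform)
- 3 v 5 days (true difference 2.0): 3.56 - 2.64 = 0.92 (intermediate)

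**Step 4: does the direction always hold?** No. If onset differs, mean 3 with Day 1 onset loses 3 - 2.82 = 0.18 day, while mean 2 with Day 5 onset loses 2 - 1.75 = 0.25 day.

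**Step 5: does censoring repair it?** The diary cannot tell an event that ends on Day 7 from one that goes on, so an event present on Day 7 is known only to have lasted at least 8 - d days. Its last observed chance to resolve was between Day 6 and Day 7, so its contribution is 7 - d days. Intermediate pattern, m = 3: days so counted average 2.64 - 0.179 = 2.46 per event, and 2.46 / (1 - 0.179) = 3.0, the true mean. Using the full 8 - d days gives 2.64 / (1 - 0.179) = 3.2, slightly too long. The tie convention should therefore be written down.

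**The case against.** The strongest reply is that the target may be days with the reaction inside the window. The Safety Assessments text scopes systemic duration through Day 7, and duration is not part of the secondary endpoint, which is frequency and severity. For that target the figure is not biased, and the defect reduces to a missing label. This stands in part: the table titles give no window, so at the least the label is needed.

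The plan also does not conceal long events altogether. Counts of subjects by duration are planned, daily entries are listed (Listings 16.2.6.3 to 16.2.6.8), and Protocol 9.9 asks for follow-up of AEs continuing at study completion. The eCRF, the diary screens and the table shells are not available, so a stop-date field may exist; what can be said is that the SAP text uses none. If the SAP 4.11 imputation is applied to duration, it may lengthen events within the window, so the net bias also depends on diary completeness. All of this stands.

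A reader might infer more than the documents support:

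- **That the cellulitis-like endpoint is affected.** It is defined by concurrent Grade 3 findings, not by duration, has its own unscheduled visit, and is tabulated through the Exit Visit (Protocol 8.4.3, SAP 4.7.4.3).
- **That the longer-lasting vaccine is always the one understated most.** This needs similar onset timing (Step 4), and no document says either vaccine's reactions last longer.
- **That the protocol promises local-reaction duration throughout.** Only the Synopsis sentence quoted above does so.

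**Conclusion.** The cap is a direct consequence of SAP 4.7.4.2. The planned mean durations are biased low for total duration, and with similar onset timing in both arms any difference between vaccines shrinks. The size is unknown and the figures above are illustrative only. Under geometric durations, a true mean of 2 days appears as 1.7-2.0, 3 days as 2.2-2.8 and 5 days as 2.7-3.9; with early onset and a 2-day mean the loss is about 0.02 day. Nothing in the documents supports any particular true mean. The summary is descriptive with no planned test, so noninferiority, power, incidence, maximum intensity and relative risks are unaffected. This is a small correction, worth making because it is cheap.

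**What to change.** In SAP 4.7.4.2 and the shells for Tables 14.3.1.4.x and 14.3.1.5.x:

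1. Report by arm the number and percentage of events with severity at least 1 on Day 7.
2. Treat those events as right-censored at Day 7, stating that they lasted at least 8 - d days, and say how a blank Day 7 entry is handled.
3. Replace the mean with a Kaplan-Meier median. Name the unit: the event, or the first event per subject, since one subject can have several.
4. Label any mean that is kept as duration within Days 1-7.

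Optionally, add to Protocol 8.4.3 a resolution date for such events, taken at the diary review already held at Visit 2 or the Exit Visit, and run duration to that date.

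Cost: items 1 to 4 use data already collected and need SAP wording and slightly more programming. A median in whole days is coarse, and the Kaplan-Meier estimate assumes that duration does not depend on onset day. The optional date is one extra field; it is recalled about three weeks or more after Day 7 and is less exact than a daily diary entry.

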**Solicited Local Reactions**

Reaction	Grading			
	0	1	2	3
Pain at the vaccination site	None	For subjects less than 36 months of age at the time of the first dose of study vaccine:		
		Minor reaction on touch	Cried/protested on touch	Cried when limb was moved/spontaneously painful
		For subjects 36 months of age and older at the time of the first dose of study vaccine:		
		Does not interfere with daily activities	Interferes with daily activities	Prevents daily activity
Redness at the vaccination site (erythema)	Absent	< 10 mm	≥ 10 to ≤ 30 mm	> 30 mm
Induration/Swelling at the vaccination site	Absent	< 10 mm	≥ 10 to ≤ 30 mm	> 30 mm

**Solicited Systemic AEs**

Symptom	Grading			
	0	Mild (Grade 1)	Moderate (Grade 2)	Severe (Grade 3)
Fever	<99.5°F (<37.5°C)	≥99.5 – <100.4°F (≥37.5 – <38.0°C)	≥100.4 – <101.3°F (≥38.0 – <38.5°C)	≥101.3°F (≥38.5°C)
Nausea and/or Vomiting	None	Adverse events easily tolerated by the subject, causing minimal discomfort and does not interfere with daily activities	Adverse event sufficiently discomfoting to interfere with daily activities	Adverse event prevents normal everyday activities or requires significant medical intervention
Diarrhea				
For subjects less than 36 months of age at the time of the first dose of study vaccine:				
Loss of appetite	None	Adverse events easily tolerated by the subject, causing minimal discomfort and does not interfere with daily activities	Adverse event sufficiently discomfoting to interfere with daily activities	Adverse event prevents normal everyday activities or requires significant medical intervention
Irritability				
For subjects 36 months of age and older at the time of the first dose of study vaccine:				
Malaise and fatigue	None	Adverse events easily tolerated by the subject, causing minimal discomfort and does not interfere with daily activities	Adverse event sufficiently discomfoting to interfere with daily activities	Adverse event prevents normal everyday activities or requires significant medical intervention
Headache				
Myalgia				

#### 4.7.4.3 Cellulitis-like Reaction

Cellulitis-like reaction is defined as concurrent:

- Grade 3 injection site pain;
- Grade 3 injection site erythema/redness;
- Grade 3 injection site induration/swelling.

The number and percentage of subjects experiencing cellulitis-like reaction will be presented with 95% CIs. The relative risk and 95% CIs will also be presented for Seqirus QIV/Comparator QIV.

The number and percentage of subjects with Cellulitis-like reaction during the time period Day 1 to Day 7, and Day 1 to Day 29/Exit Visit after each vaccination (1st and 2nd), and after any vaccination will be presented.

#### 4.7.4.4 Unsolicited Adverse Events

Unsolicited AEs will be coded using MedDRA v19. The number (and percentage) of subjects experiencing at least one event (ie, the incidence) of unsolicited AEs will be summarized by MedDRA system organ class (SOC) and preferred term (PT), overall and by maximum intensity. For summaries by maximum intensity, if a subject experiences more than one event in the same system organ class and preferred term, the event with the maximum intensity will be summarised. Maximum intensity will be ranked as follows: severe > moderate > mild > unknown. All summaries will be presented by treatment group (i.e. Seqirus QIV/Comparator QIV/Overall), and repeated by age strata, gender, race, and ethnicity where specified.

Summaries will be presented for:

- Any AEs
- Any AEs by maximum intensity
- Any AEs by relationship to Study Vaccine
- Any SAEs
- Any discontinuations due to AEs
- Any deaths
- Any AESIs

All tables listing events by MedDRA SOC will use the internationally agreed order of MedDRA SOCs:

- Infections and infestations
- Neoplasms benign, malignant and unspecified (incl cysts and polyps)
- Blood and lymphatic system disorders
- Immune system disorders
- Endocrine disorders
- Metabolism and nutrition disorders
- Psychiatric disorders

- 
- Nervous system disorders
  - Eye disorders
  - Ear and labyrinth disorders
  - Cardiac disorders
  - Vascular disorders
  - Respiratory, thoracic and mediastinal disorders
  - Gastrointestinal disorders
  - Hepatobiliary disorders
  - Skin and subcutaneous tissue disorders
  - Musculoskeletal and connective tissue disorders
  - Renal and urinary disorders
  - Pregnancy, puerperium and perinatal conditions
  - Reproductive system and breast disorders
  - Congenital, familial and genetic disorders
  - General disorders and administration site conditions
  - Investigations
  - Injury, poisoning and procedural complications
  - Surgical and medical procedures
  - Social circumstances
  - Product issues

Only treatment emergent AEs (commencing after exposure to study treatment) will be included in the unsolicited AE and SAE summaries. Non-treatment emergent events (starting prior to exposure to study treatment) will be included in the subject listings and flagged but not included in the above summaries. Where an AE start date is partially or fully missing, and it is unclear as to whether the AE is treatment emergent, it will be assumed that it is.

All the AEs starting on the day of or before the exit visit (Day 29 + 4) will be included in the summaries of unsolicited AEs. AEs starting after the exit visit will be included in the subject listings and flagged but not included in the above summaries. Where an AE start date is partially or fully missing, and it is unclear as to whether the AE starts prior to the exit visit, it will be assumed that it does.

In the interim analysis, SAEs started after the exit visit will be excluded from the analysis. SAEs up to day of the safety follow-up call, irrespective of the date will be included in the final safety analysis.

If sufficient numbers of cases of AEs occur, more formal statistical analyses of event rates, duration or severity may be conducted.

Deaths will be presented by time period (Day 1 to Study Exit Visit, and Day 1 to Day 180 after last vaccination dose), by treatment, subject number, preferred term, and relationship.

All other AE information collected (e.g. outcome, action taken) will be listed as appropriate.

#### 4.7.5 Exploratory endpoints

The exploratory objective of the study is:

- To assess the frequency of antipyretic use in the first 7 days post-vaccination in two age strata: 6 months through to 35 months, and 36 months through 59 months, as well as overall according to treatment group.

Antipyretics are among medications coded under the WHO Drug dictionary ATC code N02B. Namely they include the following drug names:

- Ibuprofen
- Acetaminophen

The number and percentage of subjects consuming antipyretics during the time period Day 1 to Day 7 after each vaccination (1st and 2nd), and after any vaccination will be presented along with the exact 95% confidence limits and the number of medications used.

Descriptive statistics, i.e. number of observation, mean, SD, median, minimum, maximum will be presented to summarize the total days of individual antipyretics use in the subjects with antipyretics use. Summaries will be presented with the number (and percentage) of subjects by days of use.

Results will be presented by treatment, overall and by age strata.

Where a medication start date/end date is partially or fully missing, and it is unclear as to whether the medication is concomitant during the time period Day 1- Day 7 after each vaccination, it will be assumed that it is concomitant. Where it is unclear whether the medication has been taken in a day, it will be assumed that it has been taken.

